4.6 NOX66 – CURRENT DRUG DEVELOPMENT PROGRAM

This study forms part of a program of phase 1 studies designed to provide insight in to the safety and signals for efficacy of NOX66 in various cancer therapy settings, namely:

- Safety and PK of NOX66 as monotherapy
- NOX66 in combination with chemotherapy alone
- NOX66 in combination with palliative radiation therapy alone, and the effects on tumours externally targeted with radiation
- NOX66 in combination with palliative radiation therapy alone, and the effects on tumours not targeted with radiation therapy
- NOX66 in combination with radiation therapy alone, with radiation therapy being administered as brachytherapy (internal targeting of treatment)
- NOX66 in combination with chemotherapy and palliative radiation therapy

5 STUDY RATIONALE

5.1 RATIONALE FOR COMBINATION WITH RADIATION THERAPY

5.1.1 Radio-sensitisation

Many cancer patients receive radiation therapy, either as part of a treatment regimen or in the palliative setting, to reduce tumour size and manage pain and symptoms associated with end stage cancer.²⁸

The anti-cancer effect of ionizing radiation relates to its ability to cause double strand breaks in DNA, and the non-specificity of this effect means that the dosage of radiation able to be applied is self-limiting. This dosage limitation is exacerbated by the presence of factors (radio-resistance) that render some cancer cells less sensitive to the damaging effects of ionizing radiation, while normal cells are without those same factors and retain full radio-sensitivity, as discussed in Section 5.1.

The use of NOX66 as a tumour cell-specific sensitiser of radiation therapy may provide greater response to targeted radiation therapy within the tumour cells, with the tumour specific nature of NOX66 activity leading to no greater effect on non-tumour cells. As such, NOX66 is expected to increase the response to palliative dose radiation therapy, reducing target tumour size beyond those expected with palliative radiation therapy alone, with no significant increase in serious and severe adverse events.

5.1.2 Abscopal Response

An abscopal (from Latin ab-scopus, away from the target) response describes tumour regression at sites distant to an irradiated field, and is a rare event seen in patients with various types of metastatic tumours receiving palliative radiation therapy to a single metastasis. First described²⁹ over 50 years ago, the response is sufficiently rare to warrant clinical reports of individual cases, with responses in melanoma, lung cancer, kidney cancer and cutaneous lymphomas variously reported.³⁰⁻³³

In the only prospective clinical study³⁴ reported to date, 41 patients with metastatic solid cancers were treated with a combination of standard cytotoxic chemotherapy, external beam RT, and granulocyte-macrophage colony stimulating factor (GM-CSF). A maximum 2 lesions were irradiated (35 Gy in 10 fractionated doses) and the response measured by CT scan in both irradiated and non-irradiated lesions. An abscopal response was reported in 11/41 (27%) patients (4 lung cancer, 5 breast cancer, 2 thymic cancer). Two of these cases had a complete response (lung cancer) and 9 had a partial response. The median overall survival was 21 months for abscopal responders versus 8 months for the non-responders.

While the mechanism underlying this phenomenon is unknown, the results of the above study, in conjunction with a range of pre-clinical studies, points to the involvement of soluble signalling factors including tumour antigens that are hypothesized to be released by the dying irradiated tumour cells to mediate an immune response against non-irradiated lesions.^{35,36,37}

In addition to its anti-cancer effects, idronoxil also has confirmed immune-stimulatory effects.³⁸ Human peripheral blood CD56+ natural killer (NK) cells show increased lytic activity against K562 (myelogenous leukaemia cell line) in the presence of idronoxil. Also, in a mouse colon cancer (CT-26) model in which idronoxil monotherapy produced a significant anti-cancer effect, ex vivo studies showed that idronoxil activated both NK and tumour-specific tumour cell lysis. As such, it is hypothesized that NOX66 may produce an abscopal effect in treating non-irradiated lesions when combined with radiation therapy.

In this study, we will also monitor for any changes in non-irradiated lesions, to determine if NOX66 may induce an abscopal response when combined with radiation therapy.

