4 INTRODUCTION

The mainstays of oncology therapy – chemotherapy and radiation therapy – provide varying degrees of efficacy in patients with cancer, and for those with late stage metastatic disease the prognosis for patients can be very poor. A primary reason for these poor outcomes is the presence of chemo- and radio-resistance mechanisms in tumour cells.¹ This resistance leads to higher doses of chemotherapy and/or radiation therapy being required, to a point where the adverse effects (toxicity) of therapy outweighing the benefits, or that treatment no longer provides any benefit for patients. Finding a treatment that can overcome some or all of these resistance mechanisms may lead to:

- Providing therapy with clinically meaningful outcomes for patients with end stage and late stage cancers
- Improving clinical outcomes for patients undergoing established chemotherapy and radiation therapy treatment
- Allowing lower doses of chemotherapy and radiation therapy to be used in future treatment of patients, providing similar efficacy outcomes while minimizing toxicity – providing treatment for patients who may otherwise not receive treatment (e.g. frail and elderly patients)

This study will investigate the use of NOX66 - idronoxil formulated in a lipophilic base – in combination with palliative radiation therapy, in patients with end stage castrate resistant prostate cancer. The data generated, in conjunction with other early phase studies, will be used to inform the development of larger studies to investigate the efficacy and safety of NOX66 (idronoxil) in combination with radiation therapy and chemotherapy.

The key hypotheses to be tested in this study are:

- a. That idronoxil can be safely added to palliative dose radiation therapy.
- b. That idronoxil, via its selective inhibition of PI3K/Akt signalling in tumour cells, may sensitise tumours to palliative doses of radiation therapy, with efficacy signals being seen in this study.
- c. That any efficacy seen in irradiated tumours may lead to an effect on non-irradiated tumours.

Furthermore, this study will investigate three doses of NOX66 to determine if there is any difference in safety and / or efficacy signals with increasing dose and to determine the optimal dose for future radiation therapy combination studies.

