5.2 RATIONALE FOR DOSE OF NOX66

Pre-clinical studies in mice consistently found an effective chemo-sensitising (standard cytotoxic drugs) dose of idronoxil to be between 100-150 mg/kg.¹² Phase 2 metabolism in these models was observed to be significant, with 10-30% of idronoxil remaining as free drug and the remainder being excreted as the conjugated (inactive) metabolites. As such, an effective dose in rats of 20mg/kg free idronoxil has been used. This converts to an equivalent human dose of 3-4mg/kg, based on body surface area. Dosing in line with this was used for the intravenous and oral dosage formulations of idronoxil, with a dose of 1200mg being used for the Phase 3 oral study (Refer to Investigators' Brochure for further information)

Whilst the oral dose of idronoxil was found to be ineffective due to Phase 2 metabolism, these studies do show that idronoxil has minimal effect on non-tumour cells (in which deconjugation does occur and therefore the cells are exposed to active idronoxil). As such, doses in line with the oral dosing regimen have been selected for this and other phase 1 studies. NOX66 has been developed to protect idronoxil from complete Phase 2 metabolism, enabling the active ingredient to target tumour cells and, in the case of this study, sensitise the target tumours to radiation therapy.

While idronoxil displays significant anti-cancer effect in animals as a monotherapy,^{12,39} the applicants believe that its potential clinical use lies in its sensitizing abilities, which requires having the drug present in the tumour cell during the period of induction of the cytotoxic damage and the repairing process of that damage.

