7 STUDY DESIGN

This is an open-label Phase Ib dose confirmation and proof of concept study in up to 24 patients with end stage castrate resistant prostate cancer who are being considered for or undergoing palliative radiation therapy for pain and symptom management. Patients will have a minimum of one (1) lesion which is amenable to radiation therapy. Palliative RT (20Gy over 5 fractions) will be delivered to selected lesion in combination with rectally administered idronoxil (NOX66).

This study is intended to provide information regarding the safety of this treatment combination and justification for a larger Phase 2/3 study in the treatment of patients with combination of NOX66 and palliative radiation therapy.

Clinical response to treatment will be assessed by radiological CT/MRI scans, where applicable objectively measures by RECISTv1.1, by pain response as evaluated by Brief Pain Inventory Short Form, ECOG scores and by monitoring PSA as surrogate marker with overall (observable and symptomatic) response based on data review by an independent Radiation Oncology Expert Committee (ROEC). Local response will be based on investigator review of data in conjunction with ROEC.

PSA will be monitored as a surrogate marker of response and pain response will be evaluated using the Brief Pain Inventory Short Form throughout the study.

Patients will be suitable for the study as they become eligible for, and will be given, palliative radiation therapy for management of their cancer.

Three dose cohorts will be investigated in this study with dosing based on criteria outlined in section 10.2.7. The three doses of idronoxil investigated include:

- 400mg idronoxil provided as one NOX66 suppository per day
- 800mg idronoxil provided as one NOX66 suppository twice daily
- 1200mg idronoxil provided as one NOX66 suppository three times daily.

Treatment will be for one cycle of combined radiation therapy and NOX66 with follow up assessments at Week 6, Week 12, Week 24 and every 3 months for the following 18 months. All patients will be followed up for disease progression and survival information either by retrospective review of medical records or by a physical visit or by telephone follow up call.

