8 STUDY PARTICIPANTS

8.1 STUDY POPULATION

Twenty-four patients with metastatic castrate-resistant prostate cancer and scheduled to receive palliative radiation therapy for management of their disease will be enrolled into the study.

There will be no randomization or stratification in the study.

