10 STUDY PROCEDURES

10.1 OUTCOME MEASURES

The outcome measures supporting the primary objective of this study are:

- Number of events of > Grade 2 toxicity (as scored by CTCv4.03)
- Number of events of > Grade 2 toxicity considered by the investigator and / or the Sponsor as causally related to the use of NOX66 (as scored by CTCv4.03)
- The overall number of adverse events considered by the investigator and / or the Sponsor as causally related to the use of NOX66
- Incidence of dose limiting toxicities (DLT) and or maximum tolerated dose (MTD) of NOX66

The outcome measures supporting the secondary objectives of this study are:

- Where target (measurable) lesions have been identified:
 - a. Change intumour size of irradiated lesions according to RECIST1.1 criteria, as assessed by central review and by the investigator based on CT/MRI scan
 - b. Change in tumour size of target non-irradiated lesions according to RECIST1.1 criteria, as assessed by central review and by the investigator based on CT/MRI scan
 - c. Observation of change from baseline in Non-target lesions according to RECIST 1.1 criteria
- For all patients – overall assessment of change in disease state by an independent Radiation Oncology Expert Committee
- Change from baseline in pain score based on responses to BPI-SF
- Observation of change from baseline in PSA levels
- Assessment of patient via physical exam and ECOG Score

- Plasma level of idronoxil post treatment (immediate and long term (at 6 weeks))
- Duration of tumour progression free state from study treatment start date
- Duration of survival from study treatment start date

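### The design cannot separate an abscopal response from direct NOX66 activity in non-irradiated lesions, so hypothesis (c) and the Section 5.1.2 aim should be limited to describing response in those lesions

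*Combined protocol and SAP*

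**What the plan says.** **The aim.** Section 5.1.2 ends by saying that non-irradiated lesions will be watched for change "to determine if NOX66 may induce an abscopal response when combined with radiation therapy". Section 4 puts hypothesis (c) among the key hypotheses the study is to test: "That any efficacy seen in irradiated tumours may lead to an effect on non-irradiated tumours". Section 5.1.2 describes the term by location: an abscopal "response describes tumour regression at sites distant to an irradiated field". It adds that the mechanism is unknown, and then cites the idea that dying irradiated cells release signals that set off an immune response elsewhere.

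**The outcome.** Section 10.1 lists "Change in tumour size of target non-irradiated lesions according to RECIST1.1 criteria".

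**The design.** Section 7: "Treatment will be for one cycle of combined radiation therapy and NOX66". Section 8.1: "There will be no randomization or stratification in the study". The groups differ only in NOX66 dose (three sequential cohorts of 4, then 12 patients at a chosen dose).

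**What is said of the drug alone.** Section 5.2 begins a sentence "While idronoxil displays significant anti-cancer effect in animals as a monotherapy" and then says the sponsor sees its clinical use in sensitisation. Section 5.1.2 reports a single-agent effect in a mouse colon cancer model and activation of natural killer cells. The cascade in Section 4.3 runs from drug binding to cell death with no radiation step. Section 4.5 reports that, in rats, the rectally given drug spreads within tissues.

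**The concern.** Hypothesis (c) is causal: efficacy in an irradiated lesion leads to an effect elsewhere. To support it, one must show that out-of-field shrinkage depends on RT. In this study the non-irradiated lesions are also exposed to NOX66 for 13 to 16 days, so a direct drug effect and an RT-dependent effect predict the same observation. No group receives one treatment without the other.

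What is at stake is the conclusion the report may draw. Section 12.1 says signals of efficacy will be described and used to support the phase 2/3 programme. Section 5.1.2 calls abscopal responses rare enough to merit single case reports, so even one or two out-of-field responses could carry weight although RT may have contributed nothing to them.

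**Working it through.** The protocol gives no abscopal rate, effect size, alpha or power for this aim, so there is no planned figure to reproduce. The cited 11/41 is 26.8%, which agrees with the stated 27%. That study combined RT with chemotherapy and GM-CSF.

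**Step 1: which contrast is missing.** Whether NOX66 adds to RT needs an RT-alone comparison. Whether RT contributes to out-of-field response needs a NOX66-alone comparison. Section 5.1.2 offers an informal background for the first (abscopal responses are rare). Nothing in the document supplies the second.

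**Step 2: identifiability.** Let d be the probability of a direct drug response out of field and a the probability of an RT-dependent one, taken as independent. The observed rate is

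p = 1 − (1 − d)(1 − a), so a = 1 − (1 − p)/(1 − d).

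This is one equation in two unknowns. As an illustration take 6 responders in 24, p = 25% (exact 95% CI 9.8% to 46.7%):

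| Assumed d | Implied a |
|---|---|
| 0% | 1 − 0.75/1.00 = 25% |
| 5% | 1 − 0.75/0.95 = 21.1% |
| 10% | 1 − 0.75/0.90 = 16.7% |
| 25% | 1 − 0.75/0.75 = 0% |

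The confidence interval covers sampling error in p only. More patients would narrow it without separating a from d.

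**Step 3: apparent abscopal responders when a = 0.** The chance of at least one out-of-field responder among m evaluable patients is 1 − (1 − d)^m. The document does not say how many patients will have a measurable non-irradiated lesion, so both m = 24 and m = 12 are shown; d is an assumption throughout.

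| d | m = 24 | m = 12 |
|---|---|---|
| 5% | 1 − 0.95^24 = 71% | 46% |
| 10% | 1 − 0.90^24 = 92% | 72% |
| 20% | 1 − 0.80^24 = 99.5% | 93% |

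**Step 4: contrasts inside the design.** The dose cohorts do not help, because either pathway could strengthen with NOX66 dose. Comparing irradiated with non-irradiated lesions within a patient does not help either, because both are exposed to the drug. The attribution rule in Section 12.1 credits responses beyond those expected from RT alone to NOX66; it does not say whether the effect is direct or RT-dependent.

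**Step 5: would a second arm be practical?** Borrow 27% for NOX66 plus RT and assume 5%, 10% or 15% for NOX66 alone. At two-sided 5% and 80% power, with p̄ the mean of p0 and p1,

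n per arm = [1.96·√(2p̄(1 − p̄)) + 0.84·√(p0(1 − p0) + p1(1 − p1))]² / (p1 − p0)².

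For 5% against 27% this is (1.016 + 0.416)²/0.22² = 42.4, so 43. The other two give 81 and 180. With 12 per arm, power is about 30%, 18% and 11%. Splitting the 24 patients would remove the confounding but leave little power.

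**The case against.** The best defence is that this is a single-arm phase Ib study with a safety objective and descriptive analysis, in which unresolved mechanism is normal. The aim is worded with monitor and may, and no primary outcome or escalation rule depends on an abscopal label. All of that stands. It limits the importance of the point but does not supply the missing comparison, and Section 4 still lists (c) as a hypothesis to be tested.

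Several stronger readings are tempting and are not supported:

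- A reader might infer that out-of-field shrinkage will automatically be classed and reported as abscopal. No such rule exists, and the attribution rule in Section 12.1 is compatible with a direct drug effect.
- A reader might infer that Section 5.1.2 defines abscopal as caused by irradiation. It defines the term by location. The causal idea comes from hypothesis (c) and the mechanism paragraph.
- A reader might infer that NOX66 is known to work alone in patients. The evidence is preclinical. Oral idronoxil with carboplatin lacked efficacy (Sections 4.4 and 4.5). The sponsor attributes that to metabolism which NOX66 is designed to reduce, so a direct effect stays plausible without being established.
- A reader might think the outcome itself is misnamed. Sections 6.2, 10.1 and 10.4.8 already use neutral terms; the overreach is confined to hypothesis (c) and the Section 5.1.2 aim.

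**Conclusion.** The point holds in a limited form. Hypothesis (c) and the closing aim of Section 5.1.2 promise something the design cannot deliver, because RT-dependent and direct drug effects on non-irradiated lesions are fully confounded in all of the up to 24 planned patients. For any observed out-of-field response rate, the data fit an abscopal rate from zero up to that rate. This range is a statement of non-identifiability and does not estimate a bias.

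The confounding follows from the design alone. How much it matters in practice depends on the direct response rate in patients, which the document does not give; the 5% to 20% used above are assumptions. The formula in Step 2 also assumes that the two pathways act independently. Safety conclusions and dose-escalation rules are unaffected.

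**What to change.** 1. Reword hypothesis (c) in Section 4 and the last sentence of Section 5.1.2 so that the aim is to describe response in non-irradiated lesions under NOX66 plus RT, in line with Section 10.1.
2. State there and in the study report that such response may reflect direct NOX66 activity, an RT-dependent (abscopal) effect or both, and that it will not be presented as evidence of an abscopal effect in the phase 2/3 rationale.
3. Optionally, cross-tabulate in-field against out-of-field response, only in patients with measurable target lesions in both locations. The restriction matters because Section 10.4.8 allows irradiated lesions to be non-measurable sclerotic bone, judged through pain scores; without it, a missing in-field response might only reflect measurability. Out-of-field response without in-field response would count against (c). Response in both places would be uninformative, since both are exposed to the drug.
4. Make any comparison with the monotherapy study in Section 4.6 conditional on that study having collected response data. It is listed for safety and PK only, so it cannot be relied on as a comparator.

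The cost is a few sentences, at most one table from data already collected, and a weaker stated claim. No added arm is proposed.

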5.2 RATIONALE FOR DOSE OF NOX66

Pre-clinical studies in mice consistently found an effective chemo-sensitising (standard cytotoxic drugs) dose of idronoxil to be between 100-150 mg/kg.¹² Phase 2 metabolism in these models was observed to be significant, with 10-30% of idronoxil remaining as free drug and the remainder being excreted as the conjugated (inactive) metabolites. As such, an effective dose in rats of 20mg/kg free idronoxil has been used. This converts to an equivalent human dose of 3-4mg/kg, based on body surface area. Dosing in line with this was used for the intravenous and oral dosage formulations of idronoxil, with a dose of 1200mg being used for the Phase 3 oral study (Refer to Investigators' Brochure for further information)

Whilst the oral dose of idronoxil was found to be ineffective due to Phase 2 metabolism, these studies do show that idronoxil has minimal effect on non-tumour cells (in which deconjugation does occur and therefore the cells are exposed to active idronoxil). As such, doses in line with the oral dosing regimen have been selected for this and other phase 1 studies. NOX66 has been developed to protect idronoxil from complete Phase 2 metabolism, enabling the active ingredient to target tumour cells and, in the case of this study, sensitise the target tumours to radiation therapy.

While idronoxil displays significant anti-cancer effect in animals as a monotherapy,^{12,39} the applicants believe that its potential clinical use lies in its sensitizing abilities, which requires having the drug present in the tumour cell during the period of induction of the cytotoxic damage and the repairing process of that damage.

5.3 POTENTIAL RISKS

As with all products and formulations in Phase 1 development, the adverse event profile of idronoxil in the formulation of NOX66 has not been fully established.

In vitro studies have shown no binding affinity for idronoxil to healthy human cells and, as such, minimal adverse events directly due to idronoxil are expected. This has been supported

by the clinical research program of IV and oral formulations of idronoxil, where no adverse events of toxicity Grade 2 or higher have been reported.

It is expected that any adverse events observed in the study will be due to the use of the combination of NOX66 with palliative radiation therapy. Any adverse events greater than normally observed with this therapy in the patient group for this study (e.g. fatigue at level greater than Grade 2) are expected to be related to a greater efficacy of the treatment (due to the sensitizing effect of NOX66).

